6 GENERAL ANALYSIS DEFINITIONS

6.1 TREATMENTS

For regimen details refer to Section 3.1 of the CTP.

The treatments and treatment periods are defined as follows:

Table 6.1: 1 Treatment descriptions

TPATT	Long Name	Short Name
A	BI 409306 10 mg QD	10mg QD
B	BI 409306 25 mg QD	25mg QD
C	BI 409306 50 mg QD	50mg QD
D	BI 409306 25 mg BID	25mg BID
E	Placebo	Placebo

Table 6.1: 2 Definition of analyzing treatment period

Label	Interval	Start Date	Start time
Screening	Screening	Date of informed consent	00:00
Placebo Run-in (PBORI)	Run-in	Date of first administration of run-in medication	Time of first administration of run-in medication 12:00 if missing
BI 409306 10mg QD BI 409306 25mg QD BI 409306 50mg QD BI 409306 25mg BID Placebo	Treatment	Date of first administration of study medication	Time of first administration of study medication 12:00 if missing
Post-treatment	Post-treatment	Date of last intake of study drug + X+1 (see definition of X below)	00:00
Post-study	Post-study	Start date = Last contact date, defined as the maximum of (Trial completion date, last study drug intake + X) +1	00:00

Proprietary confidential information © 2017 Boehringer Ingelheim International GmbH or one or more of its affiliated companies

For safety analyses, data up to 7 days after last treatment intake will be considered as on treatment for AEs and for laboratory values. To clarify;

- Screening: starts from the date of informed consent to the date of first administration of run-in medication.
- Placebo run in period: starts from the date of first administration of run-in medication to the date of first administration of randomized study drug.
- On treatment: From the first intake of randomized study drug to last intake of randomized study drug + X days, where X=7 days for safety laboratory and AE.
- Post-treatment: From end of on-treatment period until last contact. Last contact date is defined in Table 6.1: 1. Post treatment period is not applicable for patients with last contact equal to 'last intake + X + 1 days' where X is 7 days as previously specified.
- Post study: From day after last contact defined in [Table 6.1: 1](#). If period starts at end of on-treatment period then post-treatment period is not applicable.

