6.7 BASELINE, TIME WINDOWS, AND CALCULATED VISITS

For efficacy, the baseline is defined as the pre-treatment observation at Visit 3. All other baseline variables will be observed from Visit 1.

For laboratory safety measurements, the last values prior to study drug administration will be considered as baseline values.

The midpoint between two on-treatment visits defines the end of a time window, with the midpoint being included in the time window of the preceding visit.

Table 6.7: 1 Time windows for all pre/on-treatment safety visits

Visit number	Visit label	Planned days	Interval (actual days on treatment)
1	Screening	-28	(-∞, PBORI-1]
2	Placebo Run-in period	-14	[PBORI ,TREATMENT-1]
3	Baseline	1	[NA, 1]
4a	Week 1	8	[2, 11]
4b	Week 2	15	[12, 18]
4c	Week 3	22	[19, 25]
5	Week 4	29	[26, 43]
6	Week 8	57	[44, 73]
EOT	Week 12	85	[74, 99]
FU	Follow-up	113	[100, Study drug stop date + 7 days]

These time windows are defined based on the planned number of days after the date of first administration of study drug. Reasons to base the time windows on the actual treatment start date rather than the randomization date are:

- If first intake of study drug shows a large delay by e.g. more than one week after the date of randomization, a measurement taken four weeks after randomization rather reflects the drug effect after three weeks than after four weeks and thus may underestimate the treatment effect at this visit.
- With large delays of the introduction of study drug after the randomization, the time window for the first on-treatment visit could include times the patient was not yet on study drug.

Proprietary confidential information © 2017 Boehringer Ingelheim International GmbH or one or more of its affiliated companies

Table 6.7: 2

Time windows for on-treatment efficacy measurement scheduled for each on treatment visit

Visit Number	Visit label	Planned days	Time window (actual days on treatment)	
			Start	End ^A
3	Baseline	1	NA	1 ^B
5	Week 4	29	2	57
EOT	Week 12	85	58	Study drug stop date + 7 days

A In case of premature discontinuation of the study drug an EOT Visit has to be performed. If such an EOT Visit falls into the time window of a previous visit, measurements will be assigned to this previous visit and the visit value will be determined as described below. In this case the time window for the visit that includes EOT Visit will end 7 days after the study drug stop date, including Day 7.

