B Only values taken prior to the start of treatment with randomized study drug can be considered baseline values. Time windows will be used for assignment of measurements to scheduled visits.

•

Repeated and unscheduled efficacy and safety measurements will be assigned to the nominal visits and listed in the subject data listing (SDL) according to the time windows described above.

If there are several safety laboratory values in one time window on treatment, the worst of these will be selected for the by-visit analyses.

For efficacy measurements, only one observation per time window will be selected for analysis at an on-treatment visit – the value will be selected which is closest to the protocol planned visit day. If there are two observations which have the same difference in days to the planned day or if there are two observations on the same day, the first value will be used. If an observation is available on the last day of treatment, this observation will be preferably selected over any later observation that is still within the time window.

Note: for LOCF imputation, the last observed on-treatment value will be carried forward, whether or not it was selected in the previous time window. For more details on LOCF refer to [section 6.6](#).

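### SAP Table 6.7:1: the Follow-up window cannot contain any scheduled follow-up visit, and the Week 8 window ends at day 73 where the SAP's own midpoint rule gives day 71

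*SAP*

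**What the plan says.** SAP 6.7 states how the visit windows are built: "The midpoint between two on-treatment visits defines the end of a time window", and the midpoint itself belongs to the earlier visit. Days are counted from first intake of study drug.

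Table 6.7:1 carries the title "Time windows for all pre/on-treatment safety visits". Three of its rows matter here:

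- Week 8 (Visit 6): planned day 57, interval [44, 73].
- Week 12 (EOT): planned day 85, interval [74, 99].
- Follow-up (FU): planned day 113, interval "100, Study drug stop date + 7 days".

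SAP 7.8.2 presents laboratory results by the visit labels of this table and counts laboratory values as on treatment up to 7 days after last intake. SAP 6.7 also says that where several laboratory values fall in one on-treatment window, the worst one enters the by-visit analysis.

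The protocol fixes the timing of FU in three places:

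- The Flow Chart sets it at EOT + 28 days with a window of ±3 days.
- Flow Chart footnote 11 sets it four weeks after an early-discontinuation visit, which is itself held within 7 days of last intake.
- Section 5.2.2.2 sets it 28 days after the last dose.

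The Flow Chart schedules laboratory tests, ECG and vital signs at FU.

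**The concern.** A window for a visit held about four weeks after the last dose cannot close one week after the last dose. A programmer who follows the table literally gets a Follow-up row that no scheduled FU visit can enter. The alternative is to depart from the SAP without a written rule. Laboratory data are the clearest case, because SAP 7.8.2 ties their presentation to these labels.

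The Week 8 limit breaks the rule printed just above the table. It moves days 72 and 73 from Week 12 to Week 8. A laboratory value from an early-discontinuation visit on one of those days would compete with the Visit 6 value under the worst-value rule, instead of appearing under Week 12.

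**Working it through.** **Midpoint rule.** Window end = (planned day + next planned day)/2, rounded down, using the planned days of Table 6.7:1.

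| Window | Midpoint | By the rule | In the table |
|---|---|---|---|
| Week 1 | (8 + 15)/2 = 11.5 | 11 | 11 |
| Week 2 | (15 + 22)/2 = 18.5 | 18 | 18 |
| Week 3 | (22 + 29)/2 = 25.5 | 25 | 25 |
| Week 4 | (29 + 57)/2 = 43 | 43 | 43 |
| Week 8 | (57 + 85)/2 = 71 | 71 | **73** |
| Week 12 | (85 + 113)/2 = 99 | 99 | 99 |

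The first four ends follow the rule. Day 99 matches numerically if FU day 113 is used, although the rule speaks of two on-treatment visits and FU is off drug. The efficacy cut in Table 6.7:2 also follows: (29 + 85)/2 = 57. Other ways of counting do not give 73 for Week 8. Days counted from zero give (56 + 84)/2 = 70. The upper visit limits give (60 + 88)/2 = 74. Mixing planned days with visit limits gives 69.5 or 72.5.

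**Who is touched by days 72–73.** Visit 6 is due on days 54–60 (57 ± 3) and EOT on days 85–88 (85, +3), so no scheduled on-time visit is affected. An early-discontinuation visit takes place 0 to 7 days after last intake. For it to fall on day 72 or 73, last intake must lie between 72 − 7 = 65 and day 73.

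**FU window, on-schedule completers.**

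- EOT is on day 85–88. Protocol 6.2.2 says no study drug is taken at EOT, so last intake is on day 84–87.
- Upper limit: last intake + 7 = day 91–94. The lower limit is day 100, so the interval is inverted by 6 to 9 days. Counting a last intake on the EOT day itself would move the upper limit only to day 92–95.
- Scheduled FU: EOT + 28 ± 3 runs from 85 + 25 = 110 to 88 + 31 = 119. That is 26–32 days after last intake, or 19–25 days past the limit.

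**FU window, early stoppers.** Let last intake be on day *s*.

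- Flow Chart: the discontinuation visit is on day *s* to *s* + 7, so FU is on day *s* + 25 to *s* + 38. That is 18–31 days past *s* + 7.
- Protocol 5.2.2.2, with the same ±3 days: FU is on day *s* + 25 to *s* + 31, or 18–24 days past *s* + 7.

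Under either definition FU is at least *s* + 25, which always exceeds *s* + 7. No scheduled FU visit can meet the window.

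**When the interval is not empty.** It needs *s* + 7 ≥ 100, so last intake on day 93 or later, beyond any on-schedule last dose. The planned FU day 113 enters the interval only if *s* is day 106 or later.

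**The case against.** The best defence is that the FU limit is a deliberate on-treatment cap. The table title, "Time windows for all pre/on-treatment safety visits", and its column heading refer to time on treatment, and SAP 6.1 places data after the 7-day extension in the post-treatment period. On that reading the last row only collects on-treatment values after day 99. This may explain where the limit came from, but it does not rescue the row. The row is labelled Follow-up and planned for day 113. When it is not empty, it collects values taken during dosing or within a week of it, under a label that says the opposite.

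A second objection stands in part. SAP 7.8.2 also relies on a sponsor standard for laboratory data that is not available here, and that standard may say how post-treatment values are tabulated. The SAP also lists all individual laboratory data. So no FU laboratory result is lost; what fails is its assignment to the labelled row.

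A reader might go further and infer that off-drug ECG and vital signs of early stoppers will be counted under Week 4, 8 or 12. The documents do not support that. The SAP names the extension only for laboratory and AE data ("where X=7 days for safety laboratory and AE") and applies 7 days to efficacy in Table 6.7:2. It is silent on ECG and vital signs, while the title and column heading point away from including off-drug values. Nor can one infer that FU tables for ECG or vital signs are spoiled: SAP 7.8.3 and 7.8.4 tie neither to these labels.

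**Conclusion.** Two errors in Table 6.7:1 stand. The Follow-up interval excludes every scheduled FU visit by at least 18 days and is empty for on-schedule completers. The Week 8 window ends 2 days later than the SAP's rule allows, and no reason is given.

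The matter is minor. It is confined to descriptive by-visit safety output, and only laboratory output is explicitly linked to the labels. The primary analysis and other efficacy windows, adverse event assignment, laboratory on-treatment status and laboratory listings are unaffected. The Week 8 error reaches only unscheduled or early-discontinuation values on days 72–73. How many patients that is cannot be derived from the documents.

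The conclusion assumes that visits keep to the protocol's windows and that an early-discontinuation visit takes place within 7 days of last intake. A later discontinuation visit would only push FU further past the limit.

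**What to change.** 1. Correct Week 8 to [44, 71] and EOT to [72, 99].
2. End every post-baseline on-treatment safety window at the earlier of its listed day and drug stop + 7 days.
3. Define the FU window as post-treatment, from drug stop + 8 days to last contact. This agrees with the post-treatment period of SAP 6.1.

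Steps 2 and 3 belong together. Without the cap, a completer whose last dose is on day 84 would have FU open on day 92 while EOT still runs to day 99. A patient stopping on day 30 would have FU on days 55–68, inside Week 8. Keeping nominal labels for scheduled visits would not cure this for unscheduled values.

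One sentence should cover late dosing: if last intake is on day 93 or later, days 100 to drug stop + 7 would have no row unless the EOT window extends to drug stop + 7, as Table 6.7:2 already does for efficacy.

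The cost is a change to the SAP table and its wording. No data collection changes.

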## FLOW CHART

Trial Period	Screening	Placebo Run-in Period	Treatment Period								Follow- up
			3  Baseline	4a 	4b 	4c 	5	6	EOT/ED 		
Visit	1	2									FU
Studyweeks	-7	-2		1	2	3	4	8	12	16	
Study-Day (or duration during screening/ run-in)	Duration 1-35 days	Duration at least 14 and at most 21 days after screening period	1	8	15	22	29	57	85		EOT +28
Visit window (in days)				±1	±1	±1	±3	±3	+3		±3
Patient information & informed consent signed											
Register Patient in IRT	X										
Randomisation (via IRT)				X							
Demographics	X										
Medical history / baseline conditions	X										
In-/exclusion criteria	X	X	X								
Imaging of the Brain 	X										
Concomitant medications	X	X	X	X	X	X	X	X	X	X	
Height (screening only)/weight	X								X	X	
Vital signs	X		X	X	X 	X 	X	X	X	X	
Post Dose Heart Rate Procedure 			X								
Physical examination	X									X	
Neurological examination	X									X	
Resting ECG (digital)	X		X	X	X 	X 	X	X	X	X	
Adverse events	X	X	X	X	X 	X 	X	X	X	X	
Dispense trial medication 		X	X				X	X			
Collect study drug			X				X	X	X		
Medication Compliance Check			X				X	X	X	X	
Laboratory tests: Chemistry, haematology, urinanalysis	X		X				X	X	X	X	
Blood Glucose (Onsite) 	X		X				X			X	
Urine drug screen	X									X	
Urine pregnancy test 	X		X				X	X	X		
Vitamin B12 and folate	X									X	
RPR (FTA, if RPR positive)	X										
A-β and tau-protein assessment in CSF or amyloid deposition in PET 	X										
Prospective Suicidality Monitoring											
C-SSRS	X 	X 	X 	X 	X 	X 	X 	X 	X 	X 	

Proprietary confidential information.

© 2017 Boehringer Ingelheim International GmbH or one or more of its affiliated companies. All rights reserved.

This document may not - in full or in part - be passed on, reproduced, published or otherwise used without prior written permission.

Trial Period	Screening	Placebo Run-in Period	Treatment Period							Follow- up
			3  Baseline	4a 	4b 	4c 	5	6	EOT/ED 	
Visit	1	2								FU
Studyweeks	-7	-2		1	2	3	4	8	12	16

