7.8.2 Laboratory data

The analyses of laboratory data will be descriptive in nature and will be based on BI standards ([5](#)).

Baseline for safety laboratory parameters will be the last available measurement before the start of randomized study drug.

Laboratory measurements taken up to 7 days after the last administration of randomized study drug will be considered as on-treatment.

Only patients with at least one available on-treatment value will be included in the analysis of an individual laboratory parameter. All individual data will be presented in listings.

Study visits will be presented by the Visit labels in [Table 6.7.1](#),

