7.8.4 ECG

12-lead ECG measurements will be assessed as described in the CTP Flow Chart. ECG-findings before first intake of study drug will be considered as baseline condition. Any clinically significant new findings in the ECG measurement after the first ECG will be considered as AEs and analyzed as planned in [section 7.8.1](#).

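### The Follow-up safety window in SAP Table 6.7:1 closes before it opens, so no on-schedule Follow-up laboratory value can be assigned to that visit

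*SAP*

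**What the plan says.** SAP 6.7 sets the visit windows for safety data in Table 6.7:1, titled "Time windows for all pre/on-treatment safety visits". Days are counted from the first dose of study drug. The last two rows are:

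- EOT (Week 12): planned day 85, interval day 74 to day 99.
- Follow-up: planned day 113, interval "100, Study drug stop date + 7 days".

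SAP 6.7 also states: "Time windows will be used for assignment of measurements to scheduled visits". For laboratory data, SAP 7.8.2 adds "Study visits will be presented by the Visit labels in" this table. SAP 7.8.4 says only that "12-lead ECG measurements will be assessed as described in the CTP Flow Chart", and SAP 7.8.3 gives vital signs one line on descriptive statistics. Neither section cites the table.

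SAP 6.1 ends the on-treatment period at last intake plus X days, "where X=7 days for safety laboratory and AE". The post-treatment period starts at "Date of last intake of study drug + X+1".

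The protocol Flow Chart places EOT on day 85 (+3 days) and Follow-up at EOT + 28 days (±3), with laboratory tests, vital signs and ECG all marked at Follow-up. Protocol 6.2.2 specifies that no drug is taken at EOT. Protocol 7.3.3 undertakes to compare ECG, vital signs and other safety parameters with pre-treatment findings through to the end-of-trial evaluation. Protocol 3.1 extends formal safety evaluation to 28 days after the end of treatment.

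**The concern.** The Follow-up row does not contain its own planned day. Its lower limit belongs to a visit four weeks after treatment. Its upper limit is the cutoff that SAP 6.1 uses to end the on-treatment period. Those two limits cannot both hold for a patient who stops drug when the protocol says.

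The by-visit Follow-up summary of the safety data is at stake. A programmer who applies the table literally gets an empty Follow-up column. One who does not must choose a window that the final SAP does not supply.

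**Working it through.** **Inputs.** EOT on day 85 to 88 and Follow-up at EOT + 28 ± 3 (protocol Flow Chart). No dose at EOT (Protocol 6.2.2), so the last dose is on EOT day − 1. Window from day 100 to stop day + 7 (SAP Table 6.7:1).

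**Reproducing the table's own figures.** Planned Follow-up day: 85 + 28 = 113. Under the SAP's midpoint rule, (85 + 113)/2 = 99, so EOT ends on day 99 and Follow-up opens on day 100. Both match, so the lower limit was plainly built for a visit on day 113.

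**Upper limit for patients on schedule.** Upper limit = stop + 7. Follow-up = EOT + 25 to EOT + 31.

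| EOT day | Last dose | Window opens | Window closes | Follow-up visit | Days past the close |
|---|---|---|---|---|---|
| 85 | 84 | 100 | 91 | 110-116 | 19-25 |
| 86 | 85 | 100 | 92 | 111-117 | 19-25 |
| 87 | 86 | 100 | 93 | 112-118 | 19-25 |
| 88 | 87 | 100 | 94 | 113-119 | 19-25 |

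If a dose were taken on the EOT day itself, the close moves to day 92-95, still before day 100. Day 110-119 also lies beyond the EOT row, which ends on day 99, so the reading belongs to no row.

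**Could any stop day work?** The interval is non-empty only if stop + 7 ≥ 100, that is, stop day 93 or later. It contains day 113 only if stop + 7 ≥ 113, that is, stop day 106 or later. Even then the visit would not fit. The EOT or early discontinuation visit is never before the last dose, so Follow-up is at least stop + 25, and 25 − 7 = 18 days past the limit. A check of stop days 1 to 199, with EOT 0 to 7 days after the last dose, found no case that fits.

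**Early stoppers.** The 7-day limit is stated for laboratory and AE data only, so an off-drug ECG or vital-sign reading can fall by day count into an earlier row. For example, a last dose and discontinuation visit on day 30 give Follow-up on day 30 + 28 = 58, inside the Week 8 row (day 44 to 73).

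**After the correction.** With the window opening at stop + 8, it opens on day 92-95 for patients on schedule, and every Follow-up visit on day 110-119 falls inside it.

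**The case against.** The best defence is that the upper limit is deliberate. The table title and column head both refer to the on-treatment period, and values taken four weeks off drug should stay out of on-treatment summaries. That aim is right, but it would call for leaving the row out. It does not explain a row labelled Follow-up, with planned day 113 and a start derived from that day.

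A second objection is that the windows may not govern scheduled visits. Follow-up is a nominal visit in the Flow Chart. The general assignment sentence stands under the efficacy table, and the sentence on repeated and unscheduled measurements need not reach scheduled ones. SAP 7.8 also refers back to Protocol 7.3.3, and laboratory displays follow a sponsor standard that is not available here. So the table cannot be called the only rule for placing safety readings, and an empty column is the result of applying it as written rather than a certainty. The laboratory link still stands, because SAP 7.8.2 names the table.

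Three stronger readings are tempting, and the documents do not support them:

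- **That the SAP definitely drops Follow-up ECGs and vital signs.** SAP 7.8.3 and 7.8.4 do not cite the table. The link rests on its title covering all safety visits.
- **That the trial loses its check on reversible cardiac effects.** Protocol 2.3 describes reversible toxicology findings, generally at high dose levels. Nowhere is the Follow-up ECG given that role, and Protocol 1.2 reports that the pulse effect in humans fades quickly as concentrations fall.
- **That off-drug readings from early stoppers dilute the Week 4 to 12 means by a known amount.** A figure would need the distribution of stop days and attendance at Follow-up. The documents give neither, and the column head may be meant to keep such readings out.

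**Conclusion.** The Follow-up row is wrong as written. No Follow-up visit at its protocol time can fall in its window, whatever the stop day. For laboratory data the consequence follows directly from SAP 7.8.2: none of the on-schedule values, from up to 288 randomised patients, can be shown under Follow-up. For ECG and vital signs it follows only if the table is applied to them. The Follow-up part of the comparison in Protocol 7.3.3 would then be empty, taking its end-of-trial evaluation to include this visit.

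The severity is minor. Safety analysis is descriptive, individual laboratory values are still listed (SAP 7.8.2), and clinically relevant ECG or vital-sign changes are still recorded as adverse events (Protocol 5.2.2.1). No efficacy result changes. The early-stopper ambiguity is a small side issue and is not quantified.

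**What to change.** Change SAP wording in two places:

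1. **Table 6.7:1, Follow-up row.** Replace the interval with stop date + 8 days to last contact, whatever the study day, and take the value closest to EOT + 28 days.
2. **Table 6.7:1, on-treatment rows.** Close them at stop date + 7 days, as Table 6.7:2 already does for efficacy.
3. **SAP 6.1.** State that X = 7 days also applies to ECG and vital signs, in line with the 7-day residual effect period in Protocol 5.2.2.2. This keeps an early stopper's off-drug reading out of the Week 4, 8 and 12 rows.

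The Week 8 row can be checked in the same edit: the midpoint of days 57 and 85 is 71, but the row ends on day 73.

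No new data, visits or assessments are needed. The one small cost is that a discontinuation visit held more than 7 days after the last dose, later than the Flow Chart allows, would count as Follow-up.
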